5.3 Study Medication Supply, Preparation, and Administration

5.3.1 Study Medication Supply

The medicinal component of VentaProst, Flolan, (epoprostenol sodium), is already approved for I.V. delivery. The dosage form is a vial of 1.5 mg epoprostenol as a lyophilizate and the required pH 12 Sterile Flolan diluent per the currently approved packet insert (NDA20-444/ Supplement 24¹). Flolan and its diluent (pH 12 Sterile Diluent) are not re-formulated by Aerogen Pharma. Flolan is used with the same diluent system and reconstituted per the approved packet insert.

Flolan and diluent container closure (glass vial and stopper/crimp-pH 12 Sterile Diluent for Flolan comes in a plastic bottle for mixing) and secondary packaging (cardboard box) are not being altered, including the information on the vial and box label and the information in the approved Flolan packet insert. This preserves the approved drug labeling information per NDA 20-444.

Placebo will be a corresponding volume of 0.9% sodium chloride solution from the OSU IDS stock.

5.3.2 Study Medication Preparation

Refer to the VentaProst-COVID Pharmacy Manual for preparation of study drug solution..

Prior to use, drug solutions must be protected from light and refrigerated at 2° to 8°C (36° to 46°F) if not used immediately. Do not freeze drug solutions and discard any drug solution that has been frozen. Discard any drug solutions if refrigerated for more than 8 days. Control, (0.9% sodium chloride solution) will be placed in identical syringes and masked according OSU IDS procedures for blinded studies.

5.3.3 Study Medication Administration

In the ICU, patients will be started on study drug administered via the VentaProst delivery system at an initial dose administered at 13.6 ng/kg/min. Study Drug Study drug may be titrated up or down in 6.8 ng/kg/min increments (refer to VentaProst Pharmacy Manual) as clinically indicated to a dose range of 3.4 - 30.6 ng/kg/min. Study drug will be administered based on the pump rate calculated for the active treatment in mL/hr. Study drug can be administered up to 10 days.

 $^{^{1}\,\}underline{\text{https://www.accessdata.fda.gov/drugsatfda_docs/label/2018/020444s024lbl.pdf}}$

Table 3: Administration Titration Guidelines*

Up titration Guideline	Downward Titration / Guideline	
Start Dose: 13.6 ng/kg/min	Start Dose: 30.6 ng/kg/min	
1 st Step Up Dose (17.0)	1 st Step Down dose (23.8)	
2 nd Step Up Dose (20.4)	2 nd Step Down Dose (17.0)	
3 rd Step Up Dose (23.8)	3 rd Step Down dose (10.2)	
4 th Step Up Dose (27.2)	4 th Step Down dose (3.4)	
5 th Step Up Dose (30.6)		

^{*}All study drug will be administered per the calculated pump rate for the active treatment in ml/hr

Table 4-Example of Up Titration for male with Ideal Body Weight of 70 kg

Initial Dose Rate	Initial Pump Rate	New Dose Rate	New Pump Rate
13.6 ng/kg/min	1.89 mL/hr	13.6 ng/kg/min	1.89 mL/hr
		17.0 ng/kg/min	2.39 mL/hr
		20.4 ng/kg/min	2.86 mL/hr
		23.8 ng/kg/min	3.33 mL/hr
		27.2 ng/kg/min	3.81 mL/hr
		30.6 ng/kg/min	4.28 mL/hr

Active drug is prepared with 50 mL in each syringe at a concentration of 30,000 ng/mL. All study drug will be administered per the calculated pump rate for the active treatment in ml/hr.

5.3.4 Study Medication Weaning

Patients will be weaned from study drug slowly to avoid rebound vasoconstriction. During weaning, doses will be decreased in steps of 6.8 ng/kg/min increments, with a no less than 5 minutes between changes as clinically indicated. The weaning process should occur in isolation to other treatment changes (no changes in inotropes, vasopressors, or vasodilators) whenever possible. Patients will be observed closely before, during, and after dose changes. In the event patients demonstrate signs of hemodynamic instability or a decrease in oxygenation indicated by pulse oximetry during downward titration, the dose will be returned to its previous level. Once patients have been stable for at least 15 minutes, repeat attempts at dose reduction may be undertaken. The process will continue until patients are fully weaned. Patients will be monitored for safety and efficacy throughout study drug administration.

5.4 Identity of the Device Component of the Investigational Product

5.4.1 Identity of Device

The Phase 2a VentaProst drug delivery system is designed to accurately and precisely administer aerosol to the lungs of critically ill patients who require support via mechanical ventilation. The aerosol generator's fundamental operating mechanism and materials of construction will be similar to the 510(k)-cleared Aeroneb Solo System (K120939, K103635, K070642, Aerogen Ltd) and it is being designed for compatibility with the range of ventilators found in the OR and ICU.

5.4.1.1 VentaProst Aerosol Delivery to Ventilated Patients

The VentaProst delivery system (Figure 1) consists of reusable and single-patient use disposable elements:

- 1. Reusable multi-patient use components consist of two electronic controllers with power supplies, Aerogen Solo Nebulizer Cable, and Sensirion Flow Sensor Cable. When used together, they synchronize aerosol generation with the patient's inspiratory pattern through a single-patient use, disposable administration kit.
 - Aerogen Pro-X, is a commercially available device (K120939²) cleared for use to continuously operate the disposable Aerogen Solo nebulizer. (item #1 Figure 1).
 - Aerogen Pharma Controller (AP Controller) is an investigational device, which synchronizes aerosol generation with the ventilator inspiratory cycle (item #2 on Figure 1). This controller was tested to demonstrate its safety for use under IND129777.
 - Aerogen Solo Nebulizer Cable
 - Sensirion Flow Sensor Cable

2. Single-patient disposable kit:

- Aerogen Solo nebulizer (item #3 on Figure 1) is a commercially available, low mass and low profile vibrating mesh aerosol generator (K070642) cleared for use with the Aerogen Pro-X controller and Aerogen Continuous Nebulization Tube Set (CNTS).
- o Aerogen CNTS and syringe (items #4 and 5 on Figure 1) is a commercially available device (K103635) cleared for use to connect to the Aerogen Solo and deliver medication from the drug reservoir (syringe) to the mesh the nebulizer.
- Flow sensor and cable connected to the Aerogen Pharma Controller (AP Controller, item #7 on Figure 1). This is a new component of the system, which was tested to demonstrate safety for use in a clinical study.

The VentaProst delivery system will be used in conjunction with a commercially available and FDA-cleared syringe pump (item #8 on Figure 1). In general, any available syringe pump, which (1) is compatible with the Aerogen Continuous Nebulization Tube Set (CNTS syringe and tubing), and (2) is capable of delivering medication to the vibrating mesh nebulizer within the range of 0.4 to 12.0 mL/h as required to deliver the doses specified in the APC-VPCOV-CLN-001 Pharmacy Manual. For purposes of the VPCOV study, Aerogen Pharma will supply the Perfusor® Space Infusion Syringe Pump System from B.Braun (Figure 1). This particular syringe pump is FDA-cleared (K093913), it is compatible with the CNTS syringe (items #4 on Figure 1) and is able to

² The product names for the Aerogen commercial products changed from the term "*Aeroneb*", to the brand name "*Aerogen*". A Note to File was submitted to FDA and receipt was acknowledged by the Branch Office

deliver fluids in the rage of 0.4 to 12.0 mL/h. It is worth noting that on 11 April 2020, this pump received EUA for use in the tracheal delivery of continuous nebulized medications into a nebulizer to treat patients of all ages with or suspected of having the Coronavirus Disease 2019 (COVID-19)³.

[figure not shown]

Figure 1: Drug Delivery System

The Aerogen Pro-X (item #1, Figure 1), Aerogen Solo (item #3, Figure 1) are mounted on an I.V. pole at the patient's bedside. The two controllers and Aerogen CNTS (items #4 and 5, Figure 1) are routinely used as a system within their intended use. The sensor and nebulizer are connected into specific locations of the inspiratory limb of the ventilator pre- and post the humidifier, respectively (see Figure 2). The addition of the AP Controller and an off-the shelf Sensirion flow sensor enables the VentaProst system to synchronize aerosol delivery with the inspiratory cycle of the ventilator (Figures 1 and 2).

³ https://www.fda.gov/media/136894/download

Figure 2 illustrates the AP Controller, which is similar to the commercially available Aerogen Pro-X controller in form, size, weight and materials used for the upper and lower shells. The AP Controller uses the same AC/DC adapter and cable as used in the commercial Aerogen Pro-X controller. The packaging used for the AP Controller is same as packaging validated by Aerogen Ltd. for the commercially available Aerogen Pro-X system. Functionality of the AP Controller was tested in design verification studies (IND129777). Two dials (Figure 2) are used to: (1) set the flow threshold for nebulization triggering during the inspiratory cycle of the ventilator, accommodating initial ventilator baseline bias flows, and (2) set the duration of nebulization during the inspiratory cycle (a detailed description of the mechanism of action of the AP Controller is presented in IND129777).

[figure not shown]

Figure 2: Aerogen Pharma Controllers

Prior to administration, study drug will be prepared per the VP COVID Pharmacy Manual and placed into a 60 mL CNTS syringe. The syringe will be labeled to maintain the study blind. The user will attach the syringe to the CNTS tubing and prime the tube set so that the formulation reaches the Aerogen Solo, producing aerosol generation. The CNTS syringe set will be placed in a B Braun Perfusor Space Infusion syringe pump. The 15-mm T-Piece with nebulizer is placed between the ventilator circuit and the ETT (Figure

2). The user will select the pump rate (mL/hr) to deliver the recommended dose based on the ideal body weight in kilograms (kg) dispensed to achieve the dose rate in ng/kg/min for active treatment. The control treatment's corresponding pump flow rate in mL/hour will be calculated based on initial dose of Flolan in ng/kg/min. All study drug will be administered per the calculated pump rate for active treatment in ml/hr. The user will be able to adjust this recommended dose up or down (per protocol) by changing pump rate prior to selecting dose and initiating delivery. The selected dose will then be dispensed by the pump to the receiving surface of the mesh, resulting in generation of an aerosol with a volume median diameter in the range of 2 to 5 µm. The Aerogen Pharma Controller monitors the patient's breathing pattern and user adjusts the knob (on left) to initiate aerosol generation at the beginning of the breathing cycle. The knob on right sets the duration of aerosol generation within each breath.

The VentaProst device is designed to be compatible with standard intensive care unit (ICU) equipment. The following site-specific equipment will be needed to deliver the therapy: B.Braun syringe pump (provided by Aerogen Pharma), ventilator, endotracheal tube (ETT), humidifier, ventilator circuit. This equipment is standard for critical care medicine.

[figure not shown]

Figure 3 - VentaProst Device Placement in the Gas Pathway

5.4.2 Ventilator Settings

The device is designed for use with standard adult ventilator settings. An intermittent positive pressure ventilatory mode (i.e., not constant positive airway pressure [CPAP] or t-piece) is required to activate the device to deliver aerosol during the inspiration phase. A Heat-Moisture Exchanger (HME) may be used in the device circuit.

The site will utilize OSU's Standard of Care (SOC) mechanical ventilation guidelines for care of patients for COVID-19 with ARDS. The following ventilator parameters will be assessed daily while on VentaProst: Ventilator type, Mode, FiO₂, Inspiratory Time, Mean Airway Pressure, Peak Inspiratory Pressure, Positive End Expiratory Pressure, Respiratory Rate and Tidal Volume.

5.4.3 Device Supply

All device supplies will be provided by Aerogen Pharma Limited (including the B.Braun Syringe Pump). The serial numbers for the controllers, flow sensor, and nebulizer will also be recorded in an IP accountability dispensing log.

Used and unused devices will be inventoried and returned to the Sponsor or Sponsor's designee.

5.4.4 Device Replacement

Devices may be replaced at any time if there a suspicion of malfunction, but must be replaced if:

- The investigator suspects that, due to device malfunction, less than 90% of the total dose of study drug has been delivered. Reduced doses must be estimated and recorded in the patient's medical record and source documentation.
- The investigator suspects the device is not performing optimally for any reason.

5.4.5 Device Malfunction or Failure

One device (Aerogen Pro-X controller, Aerogen Pharma Breath Controller, Flow Sensor, Solo nebulizer, CNTS tubing and syringe, and associated components) is expected to perform throughout the duration of study treatment. If the controllers, Flow Sensor, CNTS tubing and syringe, or the Solo nebulizer are not functioning optimally for any reason, instructions for trouble-shooting provided in the device instruction for use manual should be followed. If one or more devices need to be replaced, the reason should be documented in the patient's medical record, dispensing log, and Device Performance Issues Form. Additional devices are provided for this purpose. The unique serial numbers of the new components will be recorded in the patient's medical record, dispensing log, and the source documentation.

For device malfunction or complaints, complete the Device Performance Issues Log and submit to the Sponsor at [contact] within 48 hours. Failed devices will be set aside from the general supplies, inventoried and returned to the Sponsor or the Sponsor's designee.

5.5 Blinding

Clinical and research staff and Sponsor will be blinded to Active or Control dose assignments with the exception of the pharmacy staff and an unblinded Sponsor CRA. Should unblinding be necessary, the medical monitor for this study will work with the unblinded pharmacist or unblinded CRA to unblind the patient.

Active treatment (Flolan) is clear in color when reconstituted and Control treatment (0.9% sodium chloride solution) is also clear in color to maintain the study blind. The Control and Active treatments will be placed in identical 60 mL syringes and labelled in a blinded manner prior to leaving the pharmacy.

5.6 Prior and Concomitant Therapy

For patients who receive study drug, any medication (including over-the-counter [OTC] medications or other investigational therapies) or therapy administered to the patient during the course of the study (starting at Screening and 14 days prior) will be recorded on the Prior and Concomitant Therapy data collection forms. The Investigator will record any AE on the AE data collection forms for which a concomitant medication/therapy was administered.

5.6.1 Prohibited Concomitant Therapy

Other inhaled vasodilators.

5.7 Investigational Product (IP) Supplies and Accountability

Investigational product supplies will not be sent to the Investigator(s) until the following documentation has been received by the Sponsor:

- Written proof of approval of the protocol and its informed consent forms (ICFs) by the Institutional Review Board (IRB)/Independent Ethics Committee (IEC) for the institution where the study is to be conducted. (Due to COVID-19 and the availability of the Active study medication, the study medication will be sent to the OSU pharmacy and held in quarantine until IRB approval and the completion of Study Initiation Visit (SIV), which may be conducted remotely or in person. A NTF will be sent to OSU pharmacy instructing that the study medication is not released for use until Sponsor notification.)
- An Investigator-signed and dated FDA Form 1572.
- A signed and dated curriculum vitae of the Principal Investigator including a copy of the Principal Investigator's current medical license (required in the US) or medical registration number on curriculum vitae.

The Investigator and study staff will be responsible for the accountability of all IP supplies (dispensing, inventory, and record keeping) following Aerogen Pharma instructions and adhere to Good Clinical Practice (GCP) guidelines as well as local and/or regional requirements.

Under no circumstances will the Investigator allow the IP to be used other than as directed by this protocol. IP will not be administered to any individual who is not enrolled into the study.

An accurate and timely record of the receipt of all IP; dispensing of IP to the patient; collection of unused IP; and subsequent return of unused IP to Aerogen Pharma must be maintained. This includes, but may not be limited to: (a) documentation of receipt of IP, (b) IP dispensing log, (c) IP accountability log, (d) all shipping service receipts, and (e) documentation of returned IP to the Sponsor. All forms will be provided by Aerogen Pharma. Any comparable forms that the investigational site wishes to use must be approved by Aerogen Pharma.

The supplies and inventory records must be made available, upon request, for inspection by the designated representative of Aerogen Pharma, a representative of the FDA, or a representative of a non-US health authority. All used and unused IP are to be returned to Aerogen Pharma at the conclusion of the study.

6. CRITERIA FOR EVALUATION

6.1 Primary Endpoint

- 1. Reduction of respiratory failure. Failure is defined by any one of the following:
 - Requires VV ECMO
 - Inability to extubate within 10 days or reintubation within < 24 hours
 - Change in S/F, oxygenation index and P/F ratio (≥15%) from baseline to 12 hours, Days 1, 2, 3, 4, 5, 6, 7, 8, 9 and Day 10 (or end of treatment)

or

- 2. Reduction of cardiac or circulatory failure. Failure is defined by any one of the following:
 - Need to begin inotropic therapy or 10% increase in current vasopressor therapy
 - Worsening hemodynamic parameters
 - Cardiac troponin >20% from baseline
 - BNP > 15% of baseline
 - Need for temporary mechanical circulatory support (IABP, Impella)
 - Requires VA ECMO

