Exclusion Criteria	Patients are NOT eligible for this study if they meet any of the following criteria: 1. Patients on ECMO support. 2. Patients receiving another inhalation research medication or inhaled nitric oxide. 3. Not expected to survive for 48 hours. 4. Pregnant (positive pregnancy test in a pre-dose examination) or breastfeeding 5. Open tracheostomy. 6. Clinical contra-indication, as deemed by the attending physician. 7. Allergy to Epoprostenol and its diluent 8. Using inhaled vasodilators at baseline. 9. Patients who are hemodynamically unstable as determined by investigator 10. Patients with significant hemoptysis as determined by investigator
Study Treatment(s)	Patients will receive study drug via mechanical ventilator, starting at 13.6 ng/kg/min. If determined by the treating physician, study drug can be up titrated in 3.4 ng/kg/min increments to a maximum of 30.6 ng/kg/min or down to a minimum of 3.4 ng/kg/min. At the Investigator's discretion, the patient will be weaned off the drug in 6.8 ng/kg/min increments. Study drug will be administered based on the pump rate calculated for active treatment in mL/hr. Study drug can be administered up to 10 days.
Duration of Treatment	The duration of study participation for each patient is as follows: • Screening: up to 14 days • Treatment: up to 10 days • Follow up: 28 days
Criteria for Evaluation	Primary Endpoint 1. Reduction of respiratory failure. Failure is defined by any one of the following: • Requires VV ECMO • Inability to extubate patient within 10 days or reintubation within < 24 hours • Change in S/F, oxygenation index and P/F ratio (≥15%) from baseline to 12 hours, Days 1, 2, 3, 4, 5, 6, 7, 8, 9 and Day 10 (or end of treatment) or
	 Reduction of cardiac or circulatory failure. Failure is defined by any one of the following: Need to begin inotropic therapy or 10% increase in current vasopressor therapy Worsening hemodynamic parameters Cardiac troponin > 20% from baseline BNP ≥ 15% of baseline Need for temporary mechanical circulatory support (IABP, Impella) Requires VA ECMO
	Secondary Endpoints: 1. Improvement in oxygenation defined as any one of the following: • Stabilization of PaO2/FIO2 >250 • Improvement in FIO2 by 50% or improvements ≥15% in S/F, P/F ratio from baseline at 12 hours, Day 5 and Day 10 (or end of treatment)

- 2. Improved clinical outcomes defined as one of more of the following:
 - Shorter time to extubation following the site's extubation protocol

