Chemistry (including AST, ALT, AP, T. Bili) CBC, PT/PTT	X						X					X	
Pregnancy Test (Serum or Urine)	X												
COVID-19 diagnostic test such as molecular or antigen test	X												
Cardiac Troponin, and BNP	X						X					X	
Other blood tests: fibrinogen, ferritin, LDH, Triglycerides, D-Dimer, IL-6, ESR,CRP ⁴	X						X					X	
Administer VentaProst		X	X	X	X	X	X	X	X	X	X	X	
Vital Signs ⁵	X	X	X	X	X	X	X	X	X	X	X	X	
Oxygenation Measurements ⁶		X	X	X	X	X	X	X	X	X	X	X	
Ventilator Parameters ⁷		X	X	X	X	X	X	X	X	X	X	X	
AE/SAE Monitoring		X	X	X	X	X	X	X	X	X	X	X	X
Concomitant Medications		X	X	X	X	X	X	X	X	X	X	X	X
Prone position ⁸		X	X	X	X	X	X	X	X	X	X	X	

- ¹ Informed consent may be obtained after screening study procedures that were conducted as a part of the patient's standard of care.
- ² Height only performed at screening
- ³ Chest CT or CXR may be performed anywhere from 3-8 days as clinically warranted.
- ⁴ These tests are collected only if available as Standard of Care
- ⁵ Vital signs: Prior to initiating VentaProst, Days 1-10 twice daily (morning and evening) at the same time to reduce exposure to Health Care Professionals to include; temperature, pulse rate, blood pressure.
- ⁶Continuous SpO2 via pulse oximetry
- Ventilator Parameters will be collected twice daily along with vital signs and include: Ventilator Type, Ventilator Mode, FiO₂, Inspiratory Time, Mean Airway Pressure, Peak Inspiratory Pressure, Positive End Expiratory Pressure, Tidal Volume and Respiratory Rate
- ⁸Time Prone Position 16 hours per day per OSU protocol

TABLE OF CONTENTS

INV	ESTIG.	ATOR'S SIGNATURE PAGE	3
1.	CLIN	IICAL PROTOCOL SYNOPSIS	4
TAE	BLE O	F CONTENTS	11
		ACRONYMS, ABBREVIATIONS AND	
		ION OF TERMS	14
2.	BACI	KGROUND AND RATIONALE	17
	2.1	Introduction	
	2.2	VentaProst	

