4.4 Removal of Patients from Therapy or Assessment

Aerogen Pharma or the Investigator may discontinue patients from the study at any time for safety or administrative reasons.

The End of Treatment Study procedures (Day 10) are to be completed for all patients who discontinue from the study prior to Day 10 (except Screen Failure patients).

The Investigator will promptly explain to the patient or their LAR that the study will be discontinued for the patient and provide appropriate medical treatment and other necessary measures for the patient.

Patients who discontinue early from the study will be discontinued for one of these primary reasons: Adverse events, patient death, lost to follow-up, patient withdrew consent, protocol violation, lack of efficacy, investigator decision, study terminated by sponsor, screen failure, or other. Study disposition information will be collected on the Patient Disposition DCF.

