6.2 Secondary Endpoints

- 1. Improvement in oxygenation defined as any one of the following:
 - Stabilization of PaO2/FIO2 >250
 - Improvement in FIO2 by 50% or improvements ≥15% in S/F, P/F ratio from baseline at 12 hours, Day 5 and Day 10 (or end of treatment)
- 2. Improved clinical outcomes defined as one of more of the following:
 - Time to extubation following the site's extubation protocol

- Free from re-intubation
- Reduction in ICU days
- Reduction in the number of re-admissions to the ICU due to COVID-19 within 28 days
- Reduction in total hospital days
- Mortality [28 days] defined as Cardiopulmonary mortality from all causes

3. Safety and tolerability

 Monitoring of adverse events (AEs), serious adverse events (SAEs), chest CT or Chest X-rays, vital signs, ventilatory/oxygenation parameters, and laboratory tests.

6.3 Exploratory endpoints will include (where available as part of standard of care):

- Change in LDH
- Change in fibrinogen
- Change in WBC count including lymphocytes and neutrophil subsets
- Change in triglycerides
- Change in ferritin
- Change in CRP / ESR
- Change in IL-6
- Change in D-Dimer

Changes in these parameters will be assessed for each patient from baseline to end of study as well as changes between the active and control groups.

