9.1.2.4 Days 2-10 (While on study drug)

- Continue to administer study drug if clinically indicated.
- Adverse Event/SAE assessment daily
- Concomitant medication evaluation daily
- Oxygenation measurement via continuous pulse oximetry (SpO₂)
- Ventilatory parameters assessed twice daily: Ventilator Type, Vent Mode, FiO₂, Inspiratory time, Mean Airway Pressure, Peak Inspiratory Pressure, Positive End Expiratory Pressure, Tidal Volume, and Respiratory Rate
- Vital signs will be assessed twice daily in AM and PM. Efforts will be made to obtain vital signs at the same time each day. Vital signs include: temperature, pulse rate, and blood pressure.
- Time Prone Position-16 hours per day per OSU Protocol

- Chest X-ray (Days 3-8 as clinically indicated)
- Full Chemistry Panel including LFTs, CBC with Diff including neutrophils and lymphocytes, PT/PTT, troponin, and BNP(Days 5 & 10).
- Triglycerides, LDH, ferritin, fibrinogen, CRP, ESR, IL 6 and D-Dimer may be collected if the subject's condition warrants it at Days 5 and Day 10.
- Obtain weight. (Day 10 only or at end of study drug dosing)

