10.6 Criteria for Evaluation

10.6.1 Primary Efficacy Endpoint

The primary efficacy endpoint:

- 1. Reduction of respiratory failure. Failure is defined by any one of the following:
 - Requires VV ECMO
 - Inability to extubate patient within 10 days or reintubation within <24 hours
 - Change in S/F, oxygenation index and P/F ratio (\geq 15%) from baseline to 12 hours, Days 1, 2, 3, 4, 5, 6, 7, 8, 9 and Day 10 (or end of treatment)

or

- 2. Reduction of cardiac or circulatory failure. Failure is defined by any one of the following:
 - Need to begin inotropic therapy or 10% increase in current vasopressor therapy

- Worsening hemodynamic parameters
- Cardiac troponin >20 % from baseline
- BNP \geq 15% of baseline
- Need for temporary mechanical circulatory support (IABP, Impella)
- Requires VA ECMO

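### As worded, the primary endpoint counts an unchanged or halved BNP, and a clear improvement in oxygenation, as failure

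*Combined protocol and SAP*

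**What the plan says.** This refers to the most recent protocol version in the combined document. The primary endpoint has a respiratory component and a cardiac or circulatory component, and in each a single listed item is enough for failure. The list appears in the synopsis, Section 6.1 and Section 10.6.1.

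- The respiratory list includes "Change in S/F, oxygenation index and P/F ratio (≥15%) from baseline to 12 hours" and then daily to Day 10 or end of treatment.
- The cardiac list includes "BNP > 15% of baseline" in Section 6.1 and "BNP ≥ 15% of baseline" in the synopsis. Section 10.6.1 also sets BNP against "15% of baseline".
- Section 6.2, which allows treatment end in place of the last visit, counts as success "Improvement in FIO2 by 50% or improvements ≥15% in S/F, P/F ratio from baseline at 12 hours, Day 5 and Day 10".
- BNP is drawn at screening, which Section 7.1.3 makes the laboratory baseline, and again under "PT/PTT, troponin, and BNP(Days 5 & 10". Section 4.4 adds: "The End of Treatment Study procedures (Day 10) are to be completed for all patients who discontinue from the study prior to Day 10".
- For oxygenation, Table 2 schedules continuous SpO2, and its footnote says "Ventilator Parameters will be collected twice daily along with vital signs"; FiO2 and mean airway pressure are among them.
- Section 10.3 defines change only as a difference from baseline. Section 10.1 says no SAP will be developed. The synopsis plans a success-or-failure summary against Control.

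**The concern.** A BNP equal to baseline is 100% of baseline, and a halved BNP is 50%. Both are above 15%, so both meet the failure item. The neighbouring troponin item is worded as a percentage *from* baseline, so the list does not use one form throughout.

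The oxygenation item asks only for a change of at least 15%. Elsewhere direction is written out: hemodynamics must worsen, vasopressor therapy must increase, and Section 6.2 speaks of improvements. Without a direction, a patient who responds well can be a primary failure and a secondary success on the same measurement. The item also groups indices that move opposite ways: worsening lowers S/F and P/F but raises the oxygenation index as usually defined.

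Read literally, the cardiac component is met by almost everyone and cannot separate the arms, while the respiratory component labels benefit as failure. If staff infer the intended direction instead, the primary scoring rule is an unwritten judgement with no SAP behind it, and settling it after unblinding would be post hoc.

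**Working it through.** The plan gives no sample-size, power or event-rate figure to reproduce, so the check applies the written rules directly.

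**1. BNP (exact).** Let r = post-baseline BNP / screening BNP. As written, failure is r > 0.15 (Section 6.1) or r ≥ 0.15 (synopsis, Section 10.6.1).

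| r | As written | Rise of more than 15% (r > 1.15) |
|---|---|---|
| 0.10 | not failure | not failure |
| 0.50 | failure | not failure |
| 1.00 | failure | not failure |
| 1.20 | failure | failure |

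For a baseline of 200 the cut-off is 200 × 0.15 = 30. Only a fall of about 85% or more escapes.

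**2. Oxygenation, if any one index suffices.** At unchanged SpO2, S/F changes by the inverse of the FiO2 ratio. A 15% rise in S/F needs an FiO2 ratio of 1/1.15 = 0.870, a cut of about 13%. From 0.80 that is 0.80 × 0.870 = 0.696; at 0.69, 0.80/0.69 = 1.159, so S/F is up 15.9% and the patient is a failure.

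**3. Oxygenation, if all three must change.** The documents do not define the oxygenation index; assume mean airway pressure × FiO2 / PaO2. With SpO2, PaO2 and airway pressure unchanged:

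- The index falls by at least 15% when the FiO2 ratio is 0.85 or less: 0.80 × 0.85 = 0.68. There S/F and P/F rise by 0.80/0.68 − 1 = 17.6%, so all three qualify.
- FiO2 0.80 to 0.65: S/F and P/F +23% (0.80/0.65 = 1.231); index −19% (0.65/0.80 = 0.8125). All three qualify unless airway pressure rises by more than 0.85/0.8125 − 1 = 4.6%.
- FiO2 halved, one reading of the 50% improvement in Section 6.2: +100% and −50%. All three qualify unless airway pressure rises by more than 0.85/0.50 − 1 = 70%.

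Letting everything move, from an assumed start of PaO2 80, SpO2 92, FiO2 0.80 and airway pressure 15:

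| | P/F | S/F | Index | As written |
|---|---|---|---|---|
| Better: 90, 95, 0.60, 14 | +50.0% | +37.7% | −37.8% | failure |
| Worse: 70, 90, 1.00, 17 | −30.0% | −21.7% | +61.9% | failure |

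The item does not distinguish the two patients, and the first also meets the Section 6.2 success criterion at 12 hours, Day 5 or Day 10.

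**4. BNP across arms (illustration).** The documents give no BNP distribution. Assume a lognormal ratio to baseline, median 1.0 in Control and 0.5 in Active, with SD of the log 0.5 or 1.0. Use one draw, or failure at either of two draws correlated 0.5 or 0.8. Expected failures per 10 patients = 10 × the probability that the ratio exceeds the cut-off:

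| SD of log | Draws | As written: Control / Active / difference | Rise ≥15%: Control / Active / difference |
|---|---|---|---|
| 0.5 | one | 10.0 / 9.9 / 0.08 | 3.9 / 0.5 / 3.4 |
| 0.5 | two, corr. 0.5 | 10.0 / 10.0 / 0.01 | 5.5 / 0.8 / 4.7 |
| 0.5 | two, corr. 0.8 | 10.0 / 10.0 / 0.03 | 4.9 / 0.7 / 4.2 |
| 1.0 | one | 9.7 / 8.9 / 0.9 | 4.4 / 2.0 / 2.4 |
| 1.0 | two, corr. 0.5 | 9.9 / 9.6 / 0.3 | 6.1 / 3.2 / 2.9 |
| 1.0 | two, corr. 0.8 | 9.9 / 9.3 / 0.5 | 5.5 / 2.7 / 2.7 |

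**The case against.** The strongest reply is that nobody would score this way. Both items define failure, their neighbours describe deterioration, and Section 6.2 uses the same 15% for improvement, which implies the primary item means the opposite. The trial is exploratory, with about 20 patients; individual listings are planned, so patients can be rescored. The intent is indeed evident. But it is not written for these two items, and with no SAP the protocol text is the only prespecified rule for the named primary endpoint. Rescoring from listings after unblinding is the post hoc choice to avoid.

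Some narrower points stand:

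- The single word *worsening* would supply a direction for all three indices; *increase* or *decrease* alone would not. Spelling out each index is still clearer, because the oxygenation index is undefined.
- Not every patient will have a post-baseline BNP. The draws in Section 9.1.2.4 fall under a heading limited to time on study drug, Section 4.4 concerns discontinuation from the study, and early deaths may leave none. The claim is therefore limited to patients with a post-baseline value.
- The any-one reading sets aside the *and* joining the indices, which is why the all-three reading is also worked. That reading needs PaO2, and Table 2 lists no arterial sampling, so P/F and the index may be unscoreable at some listed times.
- The halving of BNP in Active is an assumption, not evidence about this drug. The definitional error does not depend on it.

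**Conclusion.** The concern holds and must be fixed: the rule as written gives wrong classifications. For BNP the result is exact and needs no assumption: any value above 15% of baseline is a failure. For oxygenation, an FiO2 reduction of about 13% at constant SpO2 is enough under the any-one reading. Under the all-three reading it is 15%, given the assumed index formula and constant SpO2, PaO2 and airway pressure. Across arms, under the stated lognormal assumptions, the wording leaves a difference of 0.01 to 0.9 BNP failures per 10 patients, against 2.4 to 4.7 with a 15% rise. These are literal results; they do not show that the sponsor would score patients this way.

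**What to change.** Amend the protocol in writing before unblinding, keeping the sponsor's 15% thresholds:

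- **BNP:** an increase of ≥15% from baseline. This also settles the difference between > in Section 6.1 and ≥ in the synopsis and Section 10.6.1, which may be only a PDF-reading effect.
- **Oxygenation:** a decrease of ≥15% in S/F, a decrease of ≥15% in P/F, and an increase of ≥15% in oxygenation index. Define the index, and have the sponsor state whether any one or all three must worsen.
- **Consistency:** identical text in the synopsis, Section 6.1 and Section 10.6.1. Adding *increase* to the troponin item at the same time is tidying only.

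The cost is one amendment with IRB approval under Section 11.2.1, covering two items in three places, with no new data or patients. This corrects direction only; it does not settle how often a 15% change arises from ordinary variation.
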